## **1.2. Study and Dose Rationale**

The specific mechanism(s) by which crisaborole exerts its therapeutic action is not well defined. In this study, skin biopsies will be collected to characterize the mechanism of action, by evaluation of efficacy and changes in key skin biomarkers, of crisaborole ointment 2% over vehicle, applied twice a day in adult subjects with AD with maximum treatable BSA of 10%. The skin biopsy samples will be analyzed using immunohistochemistry (IHC) and gene expression, which will be done using TLDA PCR for 48 genes including housekeeping genes as well as single gene PCR for a few genes that are below detection level on TLDA.

The safety and efficacy of crisaborole has been demonstrated in two phase 3 studies (AN2728-AD-301 and AN2728-AD-302) and one long term open-label study (AN2728-AD-303). The 2% dose strength of crisaborole ointment is approved in the US for the treatment of mild-moderate atopic dermatitis for subjects  $\geq 2$  years.

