## 2. STUDY OBJECTIVES AND ENDPOINTS

Primary Objective(s):	Primary Endpoint(s):

 
• To evaluate the efficacy of crisaborole ointment 2% vs vehicle in subjects with mild to moderate AD.
 
• To evaluate change in key skin biomarkers of AD in target lesions treated with crisaborole ointment 2% or vehicle.
 
	
 
• Change from baseline in TSS in target lesions treated with crisaborole ointment 2% or vehicle on Day 15.
 
• Change from baseline in key skin biomarkers of AD (S100A12, CCL17, CCL18, CCL22, K16, elafin/PI3 and IL-13 expression level) in target lesions treated with crisaborole ointment 2% or vehicle at Day 15.
 

Secondary Objective(s):	Secondary Endpoint(s):

 
• To evaluate change in other skin biomarkers of atopic dermatitis in target lesions treated with crisaborole ointment 2% or vehicle.
 
• To evaluate normalization of biomarker and gene expression levels in lesional skin treated with crisaborole ointment 2% or vehicle.
 
• To evaluate changes in AD clinical sign and symptom severity in target lesions treated with crisaborole ointment 2% or vehicle.
 
• To assess the safety and local tolerability of crisaborole ointment 2% in subjects with mild to moderate AD.
 
	
 
• Change from baseline in other skin biomarkers in target lesions treated with crisaborole ointment 2% or vehicle at Day 15.
 
• Biomarker and gene expression level in lesional skin treated with crisaborole ointment 2% or vehicle at Day 15 and levels in non-lesional skin at Baseline.
 
• Change from baseline in lesion severity as measured by TSS, ISGA, and Pruritus Numerical Rating Scale at each visit up to Day 15.
 
• The incidence of treatment emergent AEs and SAEs.
 

CCI

Abbreviations: AD = atopic dermatitis; AE = adverse event; CCI  
ISGA = Investigator's static global assessment; SAE = serious adverse event;  
TSS = total sign score.

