### Skin biopsy and biomarkers

For all subjects, one 4.5 mm skin biopsy will be collected from each target treatment area on Day 1, and Day 15. In addition, on Day 8, subjects will be offered one optional 4.5 mm skin biopsy collected from each target treatment area, to provide additional samples for analysis. The biopsies on Day 8 and Day 15 will be collected in the vicinity, but at least 1 cm distant from where the biopsies were collected at Day 1, even if the target treatment area has cleared. One additional 4.5 mm biopsy will be collected from nonlesional skin on Day 1. Each biopsy will be cut in half. One half will be used to perform reverse transcriptase (RT) PCR and gene arrays and the other half will be used for immunohistochemistry analysis and hematoxylin and eosin (H&E) staining.

Parameters studied using IHC will include epidermal thickness (performed on H&E sections), Ki-67+ cells, Keratin 16 (K16), CD3+ T-cells, CD11C+ dendritic cells (DCs), Fc Epsilon+ dendritic cells (DCs), langerin+ cells (for langerhans cells), filaggrin.

Gene expression by RT PCR panel (skin ribonucleic acid [RNA]) will include levels of the following established cytokines associated with AD: IL-13, IL-19, IL-22, IL-17A, IL-23 (p19), IL-12/23 p40.

Gene expression by TLDA RT PCR will include the levels of the following established cytokines associated with AD: IL-1B, IL-2, IL-2RA, IL-5, IL-6, IL-8, IL-9, IL-10, IL-12p35, IL-12/23p40, IL-13, IL-15, IL-15RA, IL-17A, IL-17F, IL-19, IL-22, IL-23 (p19), IL-31, IL-32, K16, PDE4A, PDE4B, PDE4D, filaggrin, loricrin, periplakin, S100A7, S100A9, S100A12, MMP12, IFN-gamma, CXCL1, CXCL2, CXCL9, CXCL10, CCL20, elafin/PI3, hBD2, CCL13, CCL17, CCL18, CCL22, CCL26, FOXP3 and TSLP receptor, of which the following are considered the key biomarkers associated with AD pathways:

**S100A12** (general inflammation); **Keratin 16** (epidermal hyperplasia; proliferation marker (barrier function)); **Elafin/PI3** (Th17); **CCL17** (Th2); **CCL18** (Th2); **CCL22** (Th2); **IL13** (Th2). PDE4 expression will be quantified in the tissue by TLDA.

Gene arrays using Affymetrix UPlus 2 arrays will also be performed to allow for more global analyses of genomic changes and normalization of lesional samples towards non-lesional samples with treatment.

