### **9.3. Analysis of Biomarker Endpoints**

In addition to the key biomarkers, the other biomarkers endpoints in this study include (but may not be limited to) the following:

Parameters studied using immunohistochemistry (IHC) will include epidermal thickness (H&E staining), Ki-67+ cells, CD3+ T-cells, CD11c+ dendritic cells (DCs), FcEpsilonRI+ DCs, langerin+ cells, and FLG+ (filaggrin) cells. Gene expression endpoints from RT PCR or Gene array will include MMP12, IL-1B, IL-2, IL-2RA, IL-5, IL-6, IL-8, IL-9, IL-10,

IL-12p35, IL-15, IL-15RA, IL-17A, IL-17F, IL-19, IL-22, IL-31, IL-32, IL-23p19, IL-12/23p40, INF- $\gamma$ , CXCL1, CXCL2, CXCL9, CXCL10, CCL13, CCL20, CCL26, S100A7, S100A9, hBD2 (human  $\beta$  Defensive 2), FLG (filaggrin), LOR (loricrin), periplakin, FOXP3, and thymic stromal lymphopoietin (TSLP) receptor. PDE4A, PDE4B, and PDE4D expression will also be quantified.

The population for the analysis of the biomarkers will be ‘per protocol’ (PP) population, which includes any subject receiving  $\geq 1$  dose of investigational product, with both Day 1 and Day 15 biopsies done, and without protocol violations that were thought to impact the biomarker expression during the vehicle controlled period. All protocol deviations will be reviewed and assessed by the study team prior to database release. In general, all data will be summarized using descriptive statistics. No imputation will be made for missing data.

Comparison of pre- and post- treatment of skin treated with crisaborole ointment 2% or vehicle will be performed. Expression levels from RT PCR will be normalized to the housekeeping gene hARP (validated in other studies) and log2-transformed prior to analysis (reporting unit: Expression/hARP). Microarray data will be preprocessed using standard pipeline and log2 transformed expressions. Adjustments by batch effect and clinical variables will be carried out using ComBat, if needed. Mixed effect model will be used and p-values will be adjusted by Benjamini-Hochberg procedure.

Additionally, extensive bioinformatics tools will be employed to gain insights into the mechanism of action of crisaborole.

Correlation analysis will be performed to assess if change from baseline in biomarkers correlates with change in the lesion TSS.

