5. GENERAL METHODOLOGY AND CONVENTIONS

5.1. Hypotheses and Decision Rules

One of the primary analyses will be a superiority test to demonstrate crisaborole ointment 2% is more efficacious than vehicle in the target lesion in subjects with mild to moderate AD as measured by the change from baseline in target lesion severity score (TSS) between crisaborole treated lesion and vehicle treated lesion. The null hypothesis is that there is no difference between crisaborole ointment 2% and vehicle, and the alternative hypothesis is that crisaborole ointment 2% is superior to vehicle as measured by change from baseline in TSS at Day 15. The difference between crisaborole and vehicle in TSS change from baseline at Day 15 is significant if $p\text{-value} < 0.05$.

Another primary analysis is for the change in the key skin biomarkers S100A12, CCL17, CCL18, CCL22, elafin/PI3, K16, or IL-13 in the target lesion treated with crisaborole 2% ointment or vehicle. The null hypothesis is that there is no difference between crisaborole ointment 2% and vehicle in the change from baseline to Day 15 in these biomarkers, and the alternative hypothesis is that there is a difference between crisaborole ointment 2% and vehicle in the expression level of biomarkers. Mixed effect model will be used and p-values will be adjusted by Benjamini-Hochberg procedure.

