5.2.3. Analyses for Biomarkers

The skin biopsy samples will be analyzed using immunohistochemistry (IHC), gene arrays and gene expression of specific genes to elucidate the mechanism of action of Crisaborole, which will be done using Taqman Low Density Array (TLDA) PCR for 48 genes including housekeeping genes as well as single gene PCR for few genes that are below detection level on TLDA. TLDA PCR expression values are estimated by $-\Delta Ct$ that is computed relative to RPLPO housekeeping gene. Measurements under the limit of detections are imputed as 20% of the minimum value observed for that gene.

The gene expression data is modeled using a mixed effect model with Time, Tissue, and Treatment as a fixed effect and a random intercept for each patient. This formulation intrinsically models the patient correlation structure as in the case of a paired t-test, having the advantage that estimation of the main effects is possible even in the presence of missing values. This allows to use all available data at each time point rather than using only complete observations. This approach introduces less bias than restricting the analysis for those patients who completed the study. Contrasts are used to estimate the fold changes with treatment within each treatment group and conduct hypothesis testing. Changes with treatment will be estimated and per gene improvement will be defined as $-100 * (XW_{12,LS} - XW_{0,LS}) / (XW_{0,LS} - XW_{0,NL})$, $XW_{12,LS} - XW_{0,LS}$ represents the least square means for the treatment change and $XW_{0,LS} - XW_{0,NL}$ represents the least square means for the baseline differences.

The microarray data is processed using standard QC metrics and R packages. Expression measures are obtained using GCRMA algorithm. Adjustments by batch effect and clinical variables are carried out using ComBat. Probe-sets with at least 15 samples with expression

values larger than 3 are kept for further analysis. Expression values are modeled using mixed-effect models with fixed factors Time, Tissue and Treatment and a random effect for each patient. Fold changes for the comparisons of interest are estimated and hypothesis testing was conducted on such comparisons using contrasts under the general framework for linear models. P-values from the moderated (paired) t-test were adjusted for multiple hypotheses using the Benjamini–Hochberg procedure which controls the False Discovery Rate (FDR).

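### No crisaborole-vehicle contrast is visibly specified for two secondary biomarker endpoints (the 39 other PCR genes plus IHC, and normalisation); the only contrast named for PCR genes is pre/post within each treatment

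*Protocol*

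**What the plan says.** Protocol section 2 lists four secondary endpoints. The first is "Change from baseline in other skin biomarkers in target lesions treated with crisaborole ointment 2% or vehicle at Day 15". The second is "Biomarker and gene expression level in lesional skin treated with crisaborole ointment 2% or vehicle at Day 15 and levels in non-lesional skin at Baseline", which serves the objective on normalisation. Protocol section 3 adds that gene arrays are meant to show "normalization of lesional samples towards non-lesional samples with treatment".

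A between-treatment hypothesis appears in SAP 5.1 for lesion TSS and for one biomarker set: "Another primary analysis is for the change in the key skin biomarkers S100A12, CCL17, CCL18, CCL22, elafin/PI3, K16, or IL-13". SAP 6.1.2.1 gives the decision rule for those seven (adjusted p below 0.05), and SAP 6.2.2 repeats the analysis at Day 8.

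For the remaining markers the visible text is:

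- **PCR genes.** Protocol 9.3: "Comparison of pre- and post- treatment of skin treated with crisaborole ointment 2% or vehicle will be performed". SAP 5.2.3: "Contrasts are used to estimate the fold changes with treatment within each treatment group and conduct hypothesis testing". The model has Time, Tissue and Treatment as fixed effects and a random patient intercept.
- **Microarray.** SAP 5.2.3 tests comparisons of interest without naming them.
- **IHC.** The SAP names it as an assay but gives no model or test. Protocol 9.3 covers it only through its general sentences on biomarkers.
- **Normalisation.** SAP 5.2.3 defines a per-gene improvement index (treatment change as a percentage of the baseline lesional/non-lesional gap) with no test and no comparison between treatments.
- **SAP 6.2.** The visible entries cover the key biomarkers at Day 8 and their correlation with TSS. None covers the other biomarkers or normalisation at Day 15.

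**The concern.** Every subject carries a vehicle-treated lesion so that the drug's effect can be separated from that of the ointment base and of time. A pre/post test in the crisaborole lesion does not use it: it asks whether the lesion changed at all. Some shared change is plausible. Target lesions are chosen at lesion ISGA 3 or more (Protocol 4.1), and both receive a petrolatum-based ointment twice daily (Protocol 5 and 5.5).

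If only within-treatment tests are available, the natural way to describe mechanism is to list genes significant in the crisaborole lesion and not in the vehicle lesion. That compares two p-values and does not test the difference. Benjamini-Hochberg limits false rejections of the null being tested. When vehicle or time moves a gene, the pre/post null really is false, so its rejection is not an error that the procedure is built to prevent.

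At stake is what can be said about mechanism for most of the PCR panel, in a study whose purpose is mechanism.

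**Working it through.** **Number of genes.** The TLDA list in Protocol section 3 has 46 names; 46 − 7 key markers = 39. The list in Protocol 9.3 agrees: 36 genes, and then "PDE4A, PDE4B, and PDE4D expression will also be quantified", so 36 + 3 = 39.

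**The protocol's own precision figure.** Protocol 9.1 gives n = 30 and a maximal SD of 3 for the log2 change, with a 95% CI half width below 1.1. The standard error is 3/√30 = 0.548. The half width is 1.96 × 0.548 = 1.07, which reproduces the figure (1.12 with the t quantile). It applies to the change in one treated lesion, not to the crisaborole-vehicle difference.

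**Assumptions.** The documents give neither the change shared by both lesions nor the correlation between the two lesions' changes. I take a shared shift δ of 0.5, 1.0 or 1.5 log2 units, correlation ρ of 0 to 0.5, no drug effect beyond vehicle, and independent genes.

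**Pre/post test in the crisaborole lesion.** Two-sided one-sample t, 29 df, noncentrality δ/0.548 = 0.91, 1.83, 2.74. Rejection probability per gene is 14%, 42% and 75%. Over 39 genes, before rounding the probabilities, that is 5.6, 16.5 and 29.4.

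**Paired between-lesion test.** The difference in change has mean 0 whatever δ is. Its SD is 3√(2(1 − ρ)): 4.24 at ρ = 0 and 3.00 at ρ = 0.5. Rejection is 5% per gene, or 39 × 0.05 = 1.95 unadjusted. The half width would be 1.52 at ρ = 0 and 1.07 at ρ = 0.5.

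**After Benjamini-Hochberg at 5% over the 39 genes (simulation), mean number of significant genes per study:**

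| Shared shift δ | Pre/post, crisaborole lesion, unadjusted | Pre/post, crisaborole lesion, adjusted | Crisaborole only, adjusted | Between-lesion, adjusted |
|---|---|---|---|---|
| 0.5 | 5.6 | about 0.5 | about 0.5 | about 0.06 |
| 1.0 | 16.5 | about 8 | 5 to 6.5 | about 0.06 |
| 1.5 | 29.4 | about 27 | 6 to 8 | about 0.06 |

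Crisaborole only means significant in that lesion and not in the vehicle lesion. The lower figure in each range is for ρ = 0.5, the higher for ρ = 0.

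**Sensitivity to SD.** Protocol 9.1 calls 3 maximal. With SD 1.5, unadjusted pre/post rejection rises to 42% at δ = 0.5 and 94% at δ = 1.0. A smaller SD makes the problem larger for a given shift.

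**The case against.** A reader might infer that these endpoints are tested only pre/post, or that the SAP rules out a between-treatment test. The documents support neither reading. The pre/post wording fits the PCR genes alone; for IHC, microarray and normalisation the plan is silent or undefined. Nor can the sentence in SAP 5.2.3 be exclusive: SAP 6.1.2.1 sends the key biomarkers to that same section and expects an LS mean difference and a superiority decision from it. The contrast is unspecified, not excluded.

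Other points on that side:

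- **Endpoint wording.** The secondary endpoint is phrased like the primary one, which SAP 5.1 treats as between-treatment, so its wording does not imply a pre/post test. Likewise "changes in key skin biomarkers, of crisaborole ointment 2% over vehicle" in Protocol 1.2 refers to the key markers, which do have a between-treatment null. Both stand. The gap lies in the analysis sections.
- **Redaction.** Blocks after SAP 6.2.5 are blacked out, and the next visible heading is 6.4. The claim is therefore limited to visible text. But both endpoints are openly listed as secondary, and the biomarker methods section is readable.
- **Multiplicity.** Benjamini-Hochberg does reduce the counts: almost to nothing at a 0.5 shift and by about half at 1.0. It does little at 1.5.
- **Exploratory status.** This is Phase 2a, Protocol 9.3 describes most data as summarised descriptively, and no rule says that crisaborole-only significance means a drug effect. That lowers the stakes. Yet SAP 5.2.3 does provide for hypothesis testing, and a Treatment term in the model does not say which contrast is tested.

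**Conclusion.** The point holds as an omission. On the visible text, no crisaborole-vehicle contrast is specified for the 39 other PCR genes, IHC or normalisation, and the one contrast named for PCR genes does not separate drug from vehicle or time. Followed as written, and with no drug effect beyond vehicle, the plan would declare about 0.5, 8 or 27 of 39 genes changed in the crisaborole lesion after adjustment at shared shifts of 0.5, 1.0 and 1.5. The between-lesion test would declare under 0.1.

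These sizes rest on the assumed shift and correlation, on independent genes, and on the protocol's n = 30 and SD 3. If vehicle and time move nothing, the pre/post test keeps its nominal error rate. The seven key biomarkers are not affected, because their between-treatment null is stated. The gap should be closed before the data are analysed.

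**What to change.** Extend the between-treatment null in SAP 5.1 to the other PCR genes, IHC and microarray. State in SAP 5.2.3 that the tested contrast is the crisaborole-vehicle difference in change from baseline to Day 15, and name the microarray comparisons. Add Day 15 entries to SAP 6.2 and say which p-values form each Benjamini-Hochberg family. IHC needs its own model, of the same form.

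Report within-treatment changes and per-gene improvement descriptively, with intervals. For normalisation, report the crisaborole-vehicle difference in the SAP's improvement index with an interval, and relabel the index's time subscripts, which read W12 and W0, to this study's Day 15 and baseline. Testing signed Day 15 distance from non-lesional skin is not an adequate substitute: the non-lesional value cancels, leaving the raw Day 15 level difference, and the baseline lesional/non-lesional gap is lost.

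The cost is SAP text, one further contrast for the PCR and array models, and a short model specification for IHC. No new data are needed. The downside is that fewer genes will be declared changed.

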### **3. STUDY DESIGN**

#### **Overview**

This is a Phase 2a randomized, double-blind, vehicle-controlled study to characterize the mechanism of action, by evaluation of efficacy and changes in key skin biomarkers, of crisaborole ointment 2% in subjects with mild to moderate atopic dermatitis. After completing screening activities, including meeting eligibility criteria, approximately 40 subjects will be treated. In the double-blind treatment period, each subject will be randomly assigned to be treated with crisaborole ointment 2% for one target lesion. The other target lesion will receive vehicle.

The double-blind treatment period will last from Baseline/Day 1 to Day 15 skin biopsy collection and will include twice daily visits to the site for IP application and study assessments, where applicable. The open-label treatment period will start from the Day 15 skin biopsy collection and last until Day 43 (end of treatment/early termination); during this time, subjects will be able to treat all AD skin areas (except scalp), at home, with crisaborole ointment 2%.

Scheduled (outpatient) study visits for all subjects will occur at Screening (up to 30 days prior to Day 1/Baseline), Days 1 to 14 (twice daily), Day 15, and Day 43 (end of treatment/early termination). On Day 71 (end of study), a follow-up telephone call will be made by site staff to assess for AEs that may have occurred since the last visit.

### Skin biopsy and biomarkers

For all subjects, one 4.5 mm skin biopsy will be collected from each target treatment area on Day 1, and Day 15. In addition, on Day 8, subjects will be offered one optional 4.5 mm skin biopsy collected from each target treatment area, to provide additional samples for analysis. The biopsies on Day 8 and Day 15 will be collected in the vicinity, but at least 1 cm distant from where the biopsies were collected at Day 1, even if the target treatment area has cleared. One additional 4.5 mm biopsy will be collected from nonlesional skin on Day 1. Each biopsy will be cut in half. One half will be used to perform reverse transcriptase (RT) PCR and gene arrays and the other half will be used for immunohistochemistry analysis and hematoxylin and eosin (H&E) staining.

Parameters studied using IHC will include epidermal thickness (performed on H&E sections), Ki-67+ cells, Keratin 16 (K16), CD3+ T-cells, CD11C+ dendritic cells (DCs), Fc Epsilon+ dendritic cells (DCs), langerin+ cells (for langerhans cells), filaggrin.

Gene expression by RT PCR panel (skin ribonucleic acid [RNA]) will include levels of the following established cytokines associated with AD: IL-13, IL-19, IL-22, IL-17A, IL-23 (p19), IL-12/23 p40.

Gene expression by TLDA RT PCR will include the levels of the following established cytokines associated with AD: IL-1B, IL-2, IL-2RA, IL-5, IL-6, IL-8, IL-9, IL-10, IL-12p35, IL-12/23p40, IL-13, IL-15, IL-15RA, IL-17A, IL-17F, IL-19, IL-22, IL-23 (p19), IL-31, IL-32, K16, PDE4A, PDE4B, PDE4D, filaggrin, loricrin, periplakin, S100A7, S100A9, S100A12, MMP12, IFN-gamma, CXCL1, CXCL2, CXCL9, CXCL10, CCL20, elafin/PI3, hBD2, CCL13, CCL17, CCL18, CCL22, CCL26, FOXP3 and TSLP receptor, of which the following are considered the key biomarkers associated with AD pathways:

**S100A12** (general inflammation); **Keratin 16** (epidermal hyperplasia; proliferation marker (barrier function)); **Elafin/PI3** (Th17); **CCL17** (Th2); **CCL18** (Th2); **CCL22** (Th2); **IL13** (Th2). PDE4 expression will be quantified in the tissue by TLDA.

Gene arrays using Affymetrix UPlus 2 arrays will also be performed to allow for more global analyses of genomic changes and normalization of lesional samples towards non-lesional samples with treatment.

